7.7.2 Laboratory safety variables

Local laboratory results for serum chemistry and hematology parameters will be converted to the units below and provided in a data listing. The parameters for inclusion in listings are as follows:

Serum Chemistry	Sodium (mmol/L) Potassium (mmol/L) Chloride (mmol/L) CO2 (mmol/L) Glucose (mmol/L) Blood Urea Nitrogen (mmol/L) Creatinine (µmol/L) Alanine Aminotransferase (U/L) Aspartate Aminotransferase (U/L) Lactate Dehydrogenase (U/L) Alkaline Phosphatase (U/L) Total Protein (g/L) Albumin (g/L) Total Bilirubin (µmol/L) Direct Bilirubin (µmol/L)
Hematology	Red Blood Cells ($10^{12}/L$) White Blood Cells ($10^9/L$) Platelet Count ($10^9/L$) Hemoglobin (g/L) Hematocrit (fraction of 1) Neutrophils ($10^9/L$) Lymphocytes ($10^9/L$) Monocytes ($10^9/L$) Eosinophils ($10^9/L$) Basophils ($10^9/L$)

The listing will also include additional details as to whether the laboratory value was considered abnormal or whether it was clinically significant (Yes/No).

7.7.3 Vital signs and anthropomorphic measurements

Vital sign measurements including temperature (degrees Celsius), heart rate (beats/min), systolic blood pressure (mmHg), diastolic blood pressure (mmHg), and respiratory rate (breaths/min) will be provided in a data listing. Details will include the assessment (normal/abnormal) and clinical significance (Yes/No).

A data listing will also be provided for all measurements of Height (cm), Weight (kg), and BSA (m²) collected for a participant.

7.7.4 Physical examination

A data listing will be provided detailing the results of physical examinations. The listing will include the body system examined, the result (normal/abnormal), clinical significance (Yes/No), and any additional details.

7.7.5 Pregnancy

A data listing will be provided which contains the results of pregnancy tests conducted. The listing will contain information about whether the test was done (if N/A due to non-childbearing potential, the reason for non-childbearing potential) and the pregnancy test result.

7.7.6 Epstein-Barr virus (EBV) antibodies and cytomegalovirus (CMV) antibodies

A data listing will contain local results for EBV IgG (negative/positive), EBV IgM (negative/positive), EBNA (negative/positive), CMV IgG (negative/positive), and CMV IgM (negative/positive).

A separate data listing will contain central lab results for EBV qPCR (IU/mL) as well as CMV qPCR (IU/mL).

7.8 Other analyses

7.8.1 Mixed Meal Tolerance Test (MMTT)

The area under the time-versus-concentration curve (AUC) of C-peptide after a 4-hour MMTT will be calculated using the trapezoidal rule. To adjust the potential different durations of the MMTT test, C-peptide AUC will first be standardized by the duration of the MMTT test for the analysis. If the C-peptide values at time -10 minutes and time 0 minutes are missing, the AUC will be set to missing for the MMTT. If fewer than two measurements are available to calculate the AUC for a MMTT, the AUC will be set to missing.

A summary table will provide descriptive statistics of the C-peptide $\ln(\text{AUC}+1)$ by visit and by prior treatment in the TN-10 trial. As historical data have shown the C-peptide AUC is right skewed, the $\ln(\text{AUC}+1)$ transformation will be applied before summarization.

The values of the MMTT results, including both untransformed and transformed AUC, will be presented in a data listing.

Graphical presentation of the $\ln(\text{AUC}+1)$ over time may be explored.

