3. Pre-treatment medications are required on Days 1-5, optional on Days 6-12.
4. Teplizumab dose: Day 1: 106 $\mu\text{g}/\text{m}^2$, Day 2: 425 $\mu\text{g}/\text{m}^2$, Days 3 to 12: 850 $\mu\text{g}/\text{m}^2$ daily.
5. These results must be reviewed prior to drug administration (see Section 8.1.2). CBC with differentials are done locally.
6. Liver function tests (ALT, AST, LDH, alkaline phosphatase, total protein, albumin, total and direct bilirubin) and chemistries (sodium, potassium, chloride, CO₂, glucose, BUN, creatine) are done locally. Day 1 samples should be obtained pre-dose.
7. Blood samples for the measurements of teplizumab trough levels and anti-drug antibodies are to be obtained within 30 minutes before study drug infusion.
8. Serology assessments include EBV IgG and IgM, EBNA, CMV IgG and IgM, HIV, HBV, and HCV are done locally. All participants, regardless of whether they are seropositive or seronegative for EBV and CMV at screening, will be tested for viral load by the central lab at the indicated visits.
9. MMTT: 4-hour samples should be collected pre-dose on Day 1. Samples will be archived for possible future pro-insulin analysis.
10. In participants who have discontinued insulin therapy, urine ketones should be checked once daily.
11. Includes samples for RNA, plasma, serum, DNA, and measurements of B and T cell numbers and function to understand the effect of therapy on the immune system and infectious disease. Day 1 samples should be obtained pre-dose.

2. Introduction

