
 To evaluate the pharmacokinetics (PK) and immunogenicity of teplizumab To evaluate whether teplizumab treatment reduces the loss of β cells, over 78 weeks (18 months), in individuals with recent diagnosis of T1D. To evaluate key clinical parameters of diabetes management, including insulin use, hemoglobin A1c (HbA1c), and clinically important hypoglycemic episodes over 78 weeks To evaluate whether treatment with teplizumab increases the frequency of exhausted T cells 	
 Levels of teplizumab in the serum and anti-drug antibodies The area under the time-versus-concentration curve (AUC) of C-peptide after a 4-hour (4h) mixed meal tolerance test (MMTT), a measure of endogenous insulin production and β cell function, over 78 weeks HbA1c levels; insulin use, defined as a daily average in units per kilogram per day (U/kg/day); and frequency of clinically important hypoglycemic episodes over 78 weeks Frequency of CD8+ TIGIT+ KLRG1+ T cells

4. Study Design

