8.3.1. Metabolic Assessments

A 4h-MMTT will be performed at study entry (Visit 1) and every 6 months. At each study visit, the amount of exogenous insulin that is being taken over the 3 days prior to the visit will be documented. HbA1c levels will be measured prior to study drug administration and at each of the designated study visits.

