7.9 Interim analysis

An interim analysis is not planned.

7.10 Changes in the statistical plans from those presented in the study protocol (if applicable)

- The protocol specifies the use of both an ITT and Safety analysis set. The SAP defines only the Safety analysis set as those participants who receive at least one dose of study drug.
- The frequency of CD8+ TIGIT+ KLRG1+ T cells will be part of a separate mechanistic analysis plan.
- The protocol specifies that comparisons will be made in C-peptide with historical controls. Due to the small number of patients enrolled in the TN-10 Extension study, these comparisons will not be performed as part of this SAP.
- The definition of adverse event of special interest (AESI) in the SAP is different from the study protocol and aligns with the AESI definition as agreed upon with FDA for the Integrated Summary of Safety (ISS) for the at-risk BLA approved in November 2022.

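### SAP 7.8.1 lets a very sparse or early-stopped mixed-meal test stand as a 4-hour C-peptide AUC, and dividing by duration does not correct it (minor)

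*SAP*

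**What the plan says.** The endpoint for the beta-cell objective (Protocol Section 3, SAP Section 2) is the C-peptide AUC from a 4-hour mixed-meal tolerance test (MMTT), followed over 78 weeks.

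SAP 7.8.1 computes it by the trapezoidal rule and then adjusts for length: "C-peptide AUC will first be standardized by the duration of the MMTT test for the analysis". It voids the AUC in two cases only. One is that the "values at time -10 minutes and time 0 minutes are missing", most plainly meaning both. The other is: "If fewer than two measurements are available to calculate the AUC for a MMTT, the AUC will be set to missing". The surviving values are transformed to ln(AUC+1) and summarised by visit and by prior TN-10 treatment. The individual data are also shown: "The values of the MMTT results, including both untransformed and transformed AUC, will be presented in a data listing".

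The protocol adds no validity rule. Section 1.3, footnote 9, says "4-hour samples should be collected pre-dose on Day 1", and Section 8.3.1 says "A 4h-MMTT will be performed at study entry (Visit 1) and every 6 months". Neither gives post-meal sampling times. SAP 7.2.2 provides no imputation for MMTT values.

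**The concern.** Two measurements do not describe a 4-hour curve that rises and falls. As written, 0 and 30 min alone, or 0 and 240 min alone, give a valid AUC. The first covers only the early rise; the second draws a straight line under the whole response.

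The standardisation shows that the SAP expects tests of unequal length, but it sets no lower limit. Dividing by observed time is right only if the sampled part has the same mean as the whole 4 hours. It does nothing for a full-length test with a hole in the middle.

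A low value at baseline would look like later preservation; a low value at follow-up would look like loss. By-visit groups are likely to be small. SAP Section 6 caps enrolment at 30, the summary is split by prior treatment, and SAP 7.10 drops the historical-control comparison with the words "Due to the small number of patients enrolled in the TN-10 Extension study". One distorted value could then visibly move a group mean.

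**Working it through.** **Inputs.** From SAP 7.8.1: the trapezoidal rule, division by duration, ln(AUC+1), a pre-meal value and at least two measurements. The documents give no C-peptide profile, post-meal sampling times, group sizes or rate of incomplete tests, and no figure to reproduce. Everything below is therefore assumed: sampling at 0, 15, 30, 60, 90, 120, 150, 180, 210 and 240 min, the -10 min value equal to the 0 min value, and six profiles (nmol/L):

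- A: 0.25, 0.30, 0.42, 0.60, 0.70, 0.72, 0.66, 0.58, 0.50, 0.43
- B: 0.10, 0.115, 0.16, 0.24, 0.29, 0.30, 0.28, 0.25, 0.21, 0.18
- C: 0.45, 0.55, 0.78, 1.15, 1.38, 1.45, 1.35, 1.20, 1.02, 0.88
- D (early peak): 0.25, 0.36, 0.55, 0.72, 0.70, 0.62, 0.53, 0.45, 0.38, 0.33
- E (late peak): 0.25, 0.27, 0.33, 0.46, 0.58, 0.68, 0.73, 0.72, 0.66, 0.58
- F (flat): 0.25, 0.26, 0.29, 0.33, 0.36, 0.37, 0.36, 0.34, 0.31, 0.29

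**Formula.** M = Σ[(c_i + c_{i+1})/2 × (t_{i+1} − t_i)] / (t_last − t_first). Error = M(sampled)/M(full) − 1.

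**Profile A in full.** The nine trapezoids are 4.125 + 5.4 + 15.3 + 19.5 + 21.3 + 20.7 + 18.6 + 16.2 + 13.95 = 135.075, so M = 135.075/240 = 0.563.

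- 0 and 30 min: (0.25 + 0.42)/2 = 0.335, error -40.5%.
- 0 and 240 min: (0.25 + 0.43)/2 = 0.340, error -39.6%.
- Complete to 120 min, then stopped: 65.625/120 = 0.547, error -2.8%.

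**All profiles (error, %).**

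| Samples available | A | B | C | D | E | F |
|---|---|---|---|---|---|---|
| 0 and 30 min | -40.5 | -44.2 | -45.1 | -24.2 | -49.2 | -17.7 |
| 0 and 240 min | -39.6 | -39.9 | -40.6 | -45.0 | -27.3 | -17.7 |
| Complete to 60 min | -26.5 | -30.7 | -30.9 | -3.8 | -40.9 | -12.4 |
| Complete to 120 min | -2.8 | -5.2 | -5.7 | +13.0 | -20.0 | -2.1 |
| Complete to 180 min | +3.6 | +2.9 | +2.7 | +9.0 | -4.9 | +1.6 |
| -10 and 0 min only | -55.6 | -57.0 | -59.8 | -52.6 | -56.2 | -23.8 |

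The last row applies only if the two pre-meal values count as two measurements. Losing one or two intermediate samples from a full-length test costs -6% to +1%.

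**Second set of assumed profiles.** Three others (fasting 0.15, 0.30 and 0.50; peaks 0.35, 0.90 and 1.90 at 120 min) agree in direction: 0 and 30 min, -36% to -49%; 0 and 240 min, -32% to -45%; complete to 120 min, -4% to -6%.

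**Effect on a group mean.** On profile A, ln(1.563) = 0.446 and ln(1.335) = 0.289, a drop of 0.158. If the other members of the group average 0.446, one 0-and-30-min test lowers the mean by 0.158/5 = 0.032 (7%) at an assumed n = 5, or 0.016 (3.5%) at n = 10.

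**A candidate rule.** Require a last sample at 180 min or later and no gap above 90 min, integrating from 0 min. Of the 511 possible patterns that include 0 min, 298 are kept, with errors of -8% to +10%. The current rule admits all 511, with errors of -55% to +14%. Of the 213 voided, 65 were within 10% on all six profiles.

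**The case against.** The strongest reply is that no document figure supports any size. Profiles, times and group sizes are all assumed, and pattern counts list possibilities, not expected frequencies. The test is specified as 4 hours, and nothing suggests that sparse tests occur. This stands: the rule's defect follows from its text, but its practical effect is unknown and may be nil.

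Second, a reader might infer that the SAP accepts a fasting-only test as a stimulated AUC. The documents do not settle that. If the -10 and 0 min values are averaged into one baseline, the pair is a single measurement and the SAP's own rule voids it. The 24% to 60% shortfall is therefore conditional on a reading. The 0-and-30-min and 0-and-240-min cases are not.

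Third, existing protection is real. SAP 7.2 reports the median, minimum and maximum beside the mean, and the listing shows each test. Duration standardisation works tolerably for a well-sampled 2-hour test on four of the six profiles. It would be wrong to treat every early-stopped test as seriously biased. None of this, however, removes a two-point test from the summary table.

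Fourth, the 180 and 90 min limits have no basis in the documents and discard some accurate tests. That also stands, and the limits should not be adopted as fixed numbers.

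**Conclusion.** The point holds as a minor one. SAP 7.8.1 states an affirmative acceptance rule that can admit values which do not estimate the 4-hour AUC, and neither standardisation nor any protocol text corrects this. On the assumed profiles the clear cases are 18% to 49% too low (0 and 30 min) and 18% to 45% too low (0 and 240 min). Well-sampled truncation at 120 min ranges from -20% to +13%.

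A reader might go further and infer that the C-peptide results are biased, or that the beta-cell objective cannot be assessed. The documents do not support that. The rate of incomplete tests is not given, the endpoint is secondary, SAP 7.2 rules out inference, and individual results can be inspected.

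**What to change.** Replace the two-measurement rule in SAP 7.8.1 with a minimum evaluable MMTT:

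- At least one pre-meal value, with the mean of the available -10 and 0 min values used as the single 0 min value. This also settles the fasting-only question.
- Post-meal samples covering most of the 4 hours, and a maximum gap between consecutive valid samples. Take both limits from the actual sampling schedule before the AUCs are seen.
- Integrate from 0 min to the last valid sample and divide by that time. A fixed start matters slightly: on the assumed profiles a full test is 1.0% to 2.4% lower when started at -10 min.
- Otherwise set the AUC to missing. Flag incomplete tests in the existing listing. A repeat summary on complete 4-hour tests is optional.

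A last sample at 180 min or later with no gap above 90 min is one workable choice on a dense schedule. On the assumed ten-time schedule it keeps all 37 full-length tests missing up to two intermediate samples, and 51 of 56 missing three. A sparser schedule needs a wider gap limit. With assumed times 0, 30, 60, 90, 120, 180 and 240 min, the 90 min limit keeps 4 of 5 full-length tests missing one intermediate sample. It voids the one missing 180 min, although that test's error is only -4.6% to +2.0%. A 120 min limit keeps 5 of 5, but the error range of all kept tests widens from -8% to +9% to -16% to +9%.

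The cost is a few SAP sentences and one derivation flag. The downside is that a few sparse or truncated tests, some of them accurate, become missing and are not imputed.

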7.8.2 HbA1c (%)

A summary table will provide descriptive statistics of HbA1c (%) by visit and by prior treatment in the TN-10 trial.

A data listing will be provided displaying results of local HbA1c (%) testing.

7.8.3 Exogenous Insulin

Exogenous average daily insulin use (unit/kg/day) in the TN-10 Extension study will be presented by visit and prior treatment in the TN-10 trial.

The average daily insulin use for a particular visit will be derived based on the 3 days of insulin recorded in the case report form prior to a visit. The body weight (kg) at the visit, if available, will be used in the calculation; otherwise, the average of the closest prior and post-visit weights will be used.

Information on exogenous insulin will be presented in a data listing. The listing will include the nominal day reported (3 days prior to visit, 2 days prior to visit, 1 day prior to visit) as well as the insulin name and dosing.

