1.3. Schedule of Events

Week	-4	1							2				4	12	26	52	78	ET		
Month	-1	1												3	6	12	18	ET		
Day	Screen ¹	1	2	3	4	5	6	7	8	9	10	11	12	28	84	182	364	546	ET	
Visit window		Not applicable												± 4 days	± 4 days	± 2 wks	± 2 wks			
Visit number	-1	1	2	3	4	5	6	7	8	9	10	11	12	13	14	15	16	17	ET	
Informed consent/assent	X																			
Inclusion/exclusion criteria review	X	X																		
Medical history	X	X	X	X	X			X						X		X	X	X	X	
Height (cm) & weight (kg)	X	X															X	X	X	
Vital signs ²	X	X	X	X	X	X	X	X	X	X	X	X	X	X	X	X	X	X	X	
Physical exam (C=Complete; P=Partial)	C	P													P	P	P	P	C	
Previous/concomitant medications	X	X	X	X	X	X	X	X	X	X	X	X	X	X	X	X	X	X	X	
Adverse event review	X	X	X	X	X	X	X	X	X	X	X	X	X	X	X	X	X	X	X	
Teplizumab dose calculation		X																		
Premedication		X	X	X	X	X	X ³													
Teplizumab administration ⁴		X	X	X	X	X	X	X	X	X	X	X	X							
Tuberculosis testing (PPD or IGRA)	X																			
Chemistry and LFTs ^{5,6}	X	X	X						X					X	X	X	X	X	X	
CBC with differential and platelets ⁵	X	X	X	X	X		X		X					X	X		X	X	X	
Teplizumab levels ⁷		X			X					X				X	X		X	X	X	
Anti-teplizumab antibodies ⁷		X			X					X				X	X		X	X	X	
EBV/CMV serology ⁸	X																			
EBV and CMV viral loads ⁸	X														X	X				
HIV, HBV, HCV serology ⁸	X																			
4h MMT ⁹		X															X	X	X	X
T1D autoantibodies	X																			
Urine pregnancy test (WOCBP only)	X	X					X							X		X	X	X	X	
Urine ketones ¹⁰																				
HbA1c	X															X	X	X	X	
Mechanistic assessments ¹¹	X	X												X		X	X	X	X	

Abbreviations: ALT=alanine aminotransferase, AST=aspartate aminotransferase, BP=blood pressure, BUN=blood urea nitrogen, CBC=complete blood count, CMV=cytomegalovirus, EBV=Epstein-Barr virus, EBNA=Epstein-Barr nuclear antigen, ET=early termination visit, HbA1c=hemoglobin A1c, HBV=hepatitis B virus,

HCV=hepatitis C virus, HIV=human immunodeficiency virus, Ig=immunoglobulin IGRA= interferon-gamma release assay, LDH=lactate dehydrogenase, MMTT= mixed-meal tolerance test, PPD=purified protein derivative, T1D=type 1 diabetes, WOCBP=women of childbearing potential

Footnotes:

1. Enrollment must occur within 4 weeks of screening.
2. Vital signs include temperature, pulse, blood pressure, and respiration. On dosing days, vital signs should be collected pre-dose, 15 minutes after the start of infusion, at the end of infusion, and 60 minutes after the end of infusion.

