If a participant has achieved a HbA1c level of $\leq 6.5\%$ with insulin use of ≤ 0.25 U/kg/day, insulin therapy can be discontinued. The participant's blood glucose and HbA1c levels should continue to be monitored per protocol, and urine ketones should be tested at home once a day. During routine blood glucose monitoring, if the participant's blood glucose level exceeds 200 mg/dL and/or urine ketone level is moderate or greater, the participant should consult with their primary physician and/or the clinical site staff for further evaluation. If the fasting blood glucose exceeds 126 mg/dL or HbA1c exceeds 6.5%, as documented by repeat testing, the resumption of insulin therapy should be considered.

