7.2.2 Imputing missing values

In general, missing values will not have any imputation, with some exceptions noted below:

Adverse Events, Prior Medications and Concomitant Medications

Partial dates for adverse event start/stop or concomitant medication start/stop will not be imputed in data listings. However, information from partial adverse event start dates may be used to determine whether an adverse event is treatment emergent. Information from partial start dates may be used to determine between prior medications and concomitant medications.

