7.8.4 Insulin Discontinuation Criteria

TN-10 Extension participants meeting insulin discontinuation criteria (defined as $\text{HbA1c} \leq 6.5\%$ and average daily insulin use ≤ 0.25 unit/kg/day) at each visit will be summarized, by prior TN-10 trial

treatment and overall. Only participants who have available HbA1c and insulin data at the relevant visit will be included in the summary.

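### When a visit has no weight, SAP 7.8.3 averages the nearest earlier and later weights without regard to elapsed time, which can misstate early U/kg/day by a few percent

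*SAP*

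**What the plan says.** Insulin use in U/kg/day over 78 weeks is part of a named secondary endpoint (Protocol Section 3, SAP Section 2).

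- **Collection of insulin.** Protocol 8.3.1: "At each study visit, the amount of exogenous insulin that is being taken over the 3 days prior to the visit will be documented".
- **Collection of weight.** In the Schedule of Events (Protocol 1.3), the height and weight row is marked at screening, at Day 1 and then in three late columns, with nothing between.
- **Derivation.** SAP 7.8.3 starts from a measured weight: "The body weight (kg) at the visit, if available, will be used in the calculation". For a visit that lacks one, the fallback rule is a two-point mean: "otherwise, the average of the closest prior and post-visit weights will be used". The SAP sets no limit on the gap between the two weights, no weighting for time, and no rule for a visit that has no later weight.
- **Use of the result.** SAP 7.8.3 presents U/kg/day by visit and prior TN-10 treatment. SAP 7.8.4 counts participants with HbA1c at or below 6.5% and insulin use at or below 0.25 U/kg/day, and says: "Only participants who have available HbA1c and insulin data at the relevant visit will be included in the summary".

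**The concern.** A plain average is right only at the midpoint of the interval between the two weights. Day 28 lies near the start of that interval, yet the rule charges it with half of the weight change over the whole interval. In a growing participant the denominator is too large and U/kg/day too small. Day 1 has its own measured weight, so the error enters the comparison of early visits with Day 1 and can look like a fall in insulin need at an unchanged dose.

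Growth is plausible: 72% of TN-10 participants were under 18 at randomisation. A participant who leaves with no further weight has no value at visits without a measured weight, because one of the two terms of the average is missing.

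**Working it through.** The documents give no figure on this point to reproduce, so the check is of the size of the error.

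**Inputs from the documents.** Visits at Days 1, 28, 84, 182, 364 and 546; insulin at each; the averaging rule. Counting cells puts the late weights at Day 364, Day 546 and ET. The MMTT row has the same run of blanks, which would put its first post-dose test at Day 364, yet Protocol 8.3.1 says: "A 4h-MMTT will be performed at study entry (Visit 1) and every 6 months". Column alignment is therefore unreliable. The alternative is weights at Days 182, 364 and 546. Both readings are carried below.

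**Assumption.** Weight changes linearly at a yearly rate g, from -3% to +20%. The documents give no growth figure.

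**Formula.** With Day 1 weight set to 1, true weight on day d is w(d) = 1 + g(d - 1)/363. The rule uses [w(1) + w(D)]/2, where D is the day of the next weight. Relative error in U/kg/day = w(d) / {[w(1) + w(D)]/2} - 1.

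For example, with g = 20%, d = 28 and D = 364: w(28) = 1 + 0.20 × 27/363 = 1.0149; the mean is (1 + 1.20)/2 = 1.10; the error is 1.0149/1.10 - 1 = -7.7%. Only 27/363 = 7.4% of the interval has passed, but half the gain is charged.

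| g per year | Day 28, next weight Day 364 | Day 28, next weight Day 182 | Day 84, next weight Day 364 | Day 84, next weight Day 182 |
|---|---|---|---|---|
| +5% | -2.1% | -0.9% | -1.3% | -0.1% |
| +10% | -4.1% | -1.7% | -2.6% | -0.2% |
| +20% | -7.7% | -3.3% | -4.9% | -0.4% |
| -3% | +1.3% | +0.5% | +0.8% | +0.1% |

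**In absolute terms (illustration).** A participant weighs 40 kg at Day 1 and 48 kg at Day 364, on a constant 16 U/day.

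- Day 1: 16/40 = 0.400 U/kg/day.
- Day 28 under the rule: 16/44 = 0.364.
- Day 28 with interpolated weight: 40 + 8 × 27/363 = 40.6 kg, giving 16/40.6 = 0.394.

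**Discontinuation count.** By cell count, HbA1c is scheduled after dosing at Days 182, 364, 546 and ET. Weight is measured at Days 364 and 546 on either reading. Day 182 is the only regular visit where the count could rest on an averaged weight. It is also the midpoint between Days 1 and 364, so the linear error there is about 0. If growth is uneven, so that 25% to 75% of a 10% yearly gain has occurred by Day 182, the error is 1.025/1.05 - 1 = -2.4% to 1.075/1.05 - 1 = +2.4%. That moves the effective 0.25 cut-off to between 0.256 and 0.244.

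**No later weight.** On the literal reading this affects participants who leave without an ET visit. On the shifted reading it also affects the ET visit itself, which would have no scheduled weight.

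**The case against.** The strongest reply is that this is small and partly uncertain. The year-long gap rests on a table row whose columns may be displaced. On the other reading, Day 84 is essentially unaffected and Day 182 needs no averaging. The upper figures need fast growth, and participants here were diagnosed after TN-10 ended, so they are older than at TN-10 randomisation; no age distribution is given for this study. The SAP performs no inferential analysis, and weights and insulin records are listed, so values can be recalculated. All of this stands and limits the size of the point. It does not defend the plain average, which is worse than interpolation on either reading.

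A reader might infer three stronger things:

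- **That the rule favours teplizumab.** The study has one arm, the same rule applies to both prior-treatment groups, and the sign of the error follows the sign of the weight change.
- **That it biases the discontinuation count.** The check above shows that it does not do so materially.
- **That participants who have stopped insulin are dropped.** SAP 7.8.3 works from insulin recorded in the case report form, SAP 7.2.2 says "In general, missing values will not have any imputation", and SAP 7.8.4 requires available insulin data. But no rule treats no insulin as missing. Protocol 8.3.1 requires the amount to be documented, zero is an amount, and a known zero needs no imputation. The SAP is silent here; it does not state an exclusion.

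**Conclusion.** The point holds for the weight rule. Early post-dose U/kg/day, chiefly at Day 28, may be misstated because the fallback weight takes no account of elapsed time. Under an assumed linear gain of 5% to 20% per year, the understatement at Day 28 is about 2% to 8% if the next weight is at Day 364, or 1% to 3% if it is at Day 182. At Day 84 it is about 1% to 5%, or at most 0.4%. With weight loss the error is an overstatement. The rule is also undefined when no later weight exists.

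No test or decision rests on these values. They are, however, the only form in which this secondary endpoint will be reported, and the correction is easy, so it should be made. The handling of participants off insulin needs a clarifying sentence; the documents do not show a bias there.

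**What to change.** In SAP 7.8.3, replace the plain average with linear interpolation by date between the nearest earlier and later weights, and use the last earlier weight when none follows. If weight does change linearly between measurements, the error falls to zero at every interpolated visit. The cost is a sentence or two and a small programming change, using weights already collected. The only downside is the assumption of linear change between measurements.

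As a clarification, state that a day documented as having no insulin counts as 0 U, is distinct from an unrecorded day, and counts as available insulin data in SAP 7.8.4. Confirm that the case report form separates zero from blank. It would also help to say how fewer than three recorded days are handled.
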